7.1 Inclusion Criteria

Inclusion criteria are as follows:

- 18 years old or older
- Have used the ADU for at least one week
- Can read and understand English (or there are translation services in place to enable communication)
- Have capacity to provide informed consent
- Do not pose too high a risk to others or themselves to participate

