- 3. Compare these characteristics to a cohort of people who receive acute crisis care without ADU input

STUDY DESIGN

This will be a cohort study. Five ADUs will be identified from the national survey carried out in WP1. We will invite people aged 18 and over who are consecutively admitted to each ADU to participate in baseline interviews and then telephone/internet follow-up 8-12 weeks after baseline, with administrative outcome data collected at 6 months.

We will invite people form the same crisis pathway to participate in the parallel non-ADU cohort. They must be receiving CRT home treatment when recruited, but could previously have been admitted to an inpatient ward during this episode.

We aim to recruit 80 people who receive ADU care and 80 people who do not, in the locality of each ADU chosen for the mixed-method case studies. This gives a total of 400 in each 'arm', and a combined total of 800.

STUDY SCHEDULE 5

At baseline, ADU staff will screen all service users consecutively admitted to their service from the start date. All service users who meet the inclusion criteria will be approached by ADU staff and asked if they are willing to be contacted by researchers to discuss participation further (except at sites where service users have already given consent to be contacted directly about research projects: in this circumstance, researchers will contact service users directly once their eligibility and any risk-related safety requirements have been established). The researchers will keep a record of potential participants to be contacted and the date and the name of the clinician with whom this was agreed. Researchers will ask the clinician who spoke to each service user to note the patient's agreement to be contacted by a researcher in their patient records. Those who agree will be contacted by a researcher with an information sheet and offer to answer any questions. Potential participants will be given at least 24 hours to consider whether they would like to take part, and then if still interested they will be consented by a researcher, who will also collect the baseline data.

Participants will be contacted by phone 8-12 weeks after baseline to be asked if they are willing to complete the questionnaire again. If so, the researcher will collect the data required from them. If a participant does not wish continue at follow up they are free to decline.

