7.2 Exclusion Criteria

We will exclude patients who are too unwell to consent, but otherwise aim to be inclusive to gain a fully representative sample, including using local interpretation facilities when necessary.

RECRUITMENT

As noted above, researchers will recruit participants. At baseline, ADU staff will screen all service users consecutively admitted to their service from the start date. All service users who meet the inclusion criteria will be approached by ADU staff and asked if they are willing to be contacted by researchers to discuss participation further (except at sites where service users have already given consent to be contacted directly about research projects: in this circumstance, researchers will contact service users directly once their eligibility and any risk-related safety requirements have been established). The researchers will keep a record of potential participants to be contacted and the date and the name of the clinician with whom this was agreed. Researchers will ask the clinician who spoke to each service user to note the patient's agreement to be contacted by a researcher in their patient records. Those who agree will be contacted by a researcher with an information sheet and offer to answer any questions. Potential participants will be given at least 24 hours to consider whether they would like to take part, and then if still interested they will be consented by a researcher, who will also collect the baseline data. Participants will be offered £20 in cash as a thank you for taking part (£10 for the baseline interview, and £10 for the follow up interview at 8-12 weeks after baseline). If participants decline this money it will be returned to the study. Participants will be contacted by phone by a researcher 8-12 weeks after baseline in order to collect follow up data. At 6 months after baseline, participant data will be collected from patient records and clinical notes.

While many people find talking about their experiences to be helpful, some people may find that completing the questionnaire brings up issues that cause emotional distress. In this case the researcher will provide immediate emotional support to the participant, offer to pause or postpone the interview, and, if the participant asks, will contact a person of the participant's choice (e.g. current care coordinator, carer, friend, family member, colleague) for them.

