We have calculated sample size to detect a 12-13% absolute reduction in the main outcome of re-admissions to the acute pathway at 6 months after baseline (using admission figures from our previous CRT research). Our CORE programme grant1 in crisis teams is powered at 80% to detect a 15% difference between trial arms (50% versus 35%). Recent data from London crisis services suggest baseline re-admission rates could be lower, at 40%. We have explored various sample size calculations, including different assumptions regarding this baseline readmission rate. These show that 310 people in each arm would afford 90% power to detect differences such as 50% versus 36.8%, 45% versus 32.0% or 40% versus 27.4%. Inflating for a design effect by 30% to accommodate the clustered study design requires 400 per arm. These numbers also afford greater than 90% power to detect an effect size or difference of 0.3 standard deviations in the client experience measure CSQ-8 (crisis team mean CSQ = 25, sd 6).

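### The only cohort inclusion list requires a week of ADU use: as written no comparator qualifies, and read as ADU-only it sets an unmatched entry threshold in one arm

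*Protocol*

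**What the plan says.** Protocol section 7.1 opens with "Inclusion criteria are as follows" and gives one list for Workpackage 2.1. It names no cohort, and its second item is "Have used the ADU for at least one week".

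The third objective of the workpackage is to "Compare these characteristics to a cohort of people who receive acute crisis care without ADU input". Section 4 plans 400 people in each cohort and gives the comparators their only specific entry condition: "They must be receiving CRT home treatment when recruited, but could previously have been admitted to an inpatient ward during this episode". No minimum time under the CRT is stated.

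For the ADU cohort, section 4 says "We will invite people aged 18 and over who are consecutively admitted to each ADU to participate in baseline interviews", without a minimum stay, and section 7.2 says the study will "otherwise aim to be inclusive to gain a fully representative sample". The screening procedure, repeated in sections 5, 6 and 8, begins "At baseline, ADU staff will screen all service users consecutively admitted to their service from the start date". No equivalent is described for CRT caseloads.

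Section 9 names the "main outcome of re-admissions to the acute pathway at 6 months after baseline" and plans logistic regression adjusted for age, gender, main diagnostic group and a severity measure.

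**The concern.** Two things are wrong with the eligibility text. First, taken literally, it shuts out half of the planned sample: someone who receives no ADU care cannot have used an ADU for a week.

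Second, the obvious repair, reading the item as ADU-only, leaves the two cohorts with different entry rules. ADU entrants who leave within seven days, because they were admitted to a ward, disengaged or recovered quickly, never become eligible. CRT patients may be recruited at any point in CRT care, so someone recruited early and admitted days later counts as a primary-outcome event.

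The comparison of readmission, and of CSQ-8, is then between people who stayed a week in one service and people with an unspecified time in the other. The planned covariates include no time-in-service term, and no covariate can restore people who are not in the data.

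**Working it through.** **The plan's own figures.** Section 9 gives 310 per arm for 90% power at 50% v 36.8%, 45% v 32.0% or 40% v 27.4%. With a two-sided 5% level (assumed; the protocol states none) and a continuity-corrected two-proportion formula, the results are 310, 308 and 310, so the figure reproduces. Inflating by 30% gives 310 × 1.3 = 403, against the stated 400. The arithmetic is sound. The target differences are 50 − 36.8 = 13.2, 45 − 32.0 = 13.0 and 40 − 27.4 = 12.6 points.

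**Entry rules side by side.**
- Minimum time in service: one week for the ADU cohort (7.1); none stated for comparators (4).
- Screening: consecutive ADU admissions (5, 6, 8); no CRT procedure described.
- Outcome clock: six months from baseline in both cohorts (8, 9). For ADU users, baseline falls after the qualifying week.

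**Size when risk depends only on time since entry.** The protocol gives no week-one exit rate or hazard, so these are assumptions: no true effect, 40% risk over 26 weeks from service entry (the lowest baseline rate in section 9), comparators recruited at CRT entry, and ADU baseline at day 7 with 26 weeks of follow-up from there. The cumulative hazard over 26 weeks is −ln(0.60) = 0.5108.
- Constant hazard: h = 0.5108/26 per week. ADU risk over weeks 1 to 27 = 1 − exp(−26h) = 40.0%. Bias 0.
- Week-one hazard three times the later hazard: 3h + 25h = 0.5108, so h = 0.5108/28 = 0.01824. ADU risk over weeks 1 to 27 = 1 − exp(−26 × 0.01824) = 1 − exp(−0.4743) = 37.8%. Bias 40.0 − 37.8 = 2.2 points in favour of the ADU.

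**Size when people differ in risk.** Let p be the six-month risk in all ADU admissions, f the share leaving in week one, and r the risk those leavers would have had on the same clock. The enrolled ADU risk is q = (p − f·r)/(1 − f). With p = 40%:
- r = 80%, f = 5%: (0.40 − 0.04)/0.95 = 37.9%, apparent benefit 2.1 points.
- r = 80%, f = 10%: (0.40 − 0.08)/0.90 = 35.6%, apparent benefit 4.4 points.
- r = 20%, f = 10%: (0.40 − 0.02)/0.90 = 42.2%, apparent harm 2.2 points.

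**CSQ-8.** If leavers would have scored d points lower, the enrolled mean rises by f·d/(1 − f). For f = 10% and d = 3 to 6 this is 0.33 to 0.67 points, or 0.06 to 0.11 of the stated SD of 6, against a target of 0.3 SD.

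**The case against.** The strongest case on the other side has four parts.

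**The literal reading is only a drafting slip.** Section 4 gives comparators their own condition and target. The same list reappears in section 16.1 for the qualitative study, whose carers and staff could not meet it either. It is evidently a list for ADU service users. This stands as far as intent goes: a reader might infer that the comparator arm cannot be recruited, and the documents do not support that. The text still needs the label, because section 4 does not lift the criterion.

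**It is not immortal time.** A reader might infer that event-free ADU time is credited as follow-up. It is not: outcomes run from baseline, which follows the qualifying week. This stands in full, and what remains is selective entry. For the same reason the shortcut (0.40 − x)/(1 − x), with x the share failing in week one, uses the wrong clock. At x = 2% it gives 38.8%, a bias of 1.2 points, although the constant hazard that implies roughly that x gives no bias.

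**Comparators are selected too.** Anyone who left CRT care before recruitment is missed, and some comparators arrive by way of a ward. This stands: the contrast is a fixed week against an unspecified delay, not a week against zero.

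**The direction is not established.** A reader might infer that the bias must favour the ADU. The week also removes quick recoverers, and the sign reverses if they predominate. This stands as well.

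None of these points supplies a matching minimum for the comparators or a CRT screening procedure.

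**Conclusion.** Two points are certain from the text: the list contradicts the design if read literally, and if read as ADU-only it puts a fixed one-week minimum on one cohort with no stated counterpart in the other. The minimum also conflicts with recruiting consecutive ADU admissions and with the aim of a representative sample.

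The resulting bias is plausible and probably favours the ADU, but neither its sign nor its size can be derived from the documents. With 40% risk, no true effect and comparators recruited at CRT entry, it runs from 0 (constant hazard) to 2.2 points (threefold week-one hazard), against a target of 12.6 to 13.2. Strong differences in risk between people could make it larger, such as 4.4 points if 10% leave early at 80% risk. If 10% leave early at 20% risk, it becomes 2.2 points against the ADU. Comparators recruited later than CRT entry would change these figures. The reason to act is that the selection is one-sided, affects the primary comparison and cannot be repaired by the planned adjustment.

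**What to change.** Amend section 7.1 and the recruitment text as follows:
- State that the one-week ADU criterion applies to the ADU cohort only.
- Give the CRT cohort its own criterion, with the same minimum time in the index service, or remove the minimum from both. Define time zero in the same way for both.
- Describe consecutive screening of CRT caseloads, parallel to that of ADU admissions.
- Reconcile section 4's consecutive-admission wording and section 7.2's representativeness aim with whichever rule is kept.
- Record the time from service start and from episode start to baseline in both cohorts. If comparators have already been recruited earlier than the minimum, run the comparison restricted to those past it.
- Count and report ADU admissions that end in the first week.

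The cost is a short protocol amendment. With a matched minimum, somewhat fewer CRT patients will be eligible and they will be approached slightly later; the protocol gives no CRT length of stay from which to say how many would be lost. Matched time in service may still not match position in the crisis episode exactly, since section 9 treats both groups as CRT cohorts and ADU users may already have spent time under the CRT. Recording episode start lets that be examined.

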7.2 Exclusion Criteria

We will exclude patients who are too unwell to consent, but otherwise aim to be inclusive to gain a fully representative sample, including using local interpretation facilities when necessary.

RECRUITMENT

As noted above, researchers will recruit participants. At baseline, ADU staff will screen all service users consecutively admitted to their service from the start date. All service users who meet the inclusion criteria will be approached by ADU staff and asked if they are willing to be contacted by researchers to discuss participation further (except at sites where service users have already given consent to be contacted directly about research projects: in this circumstance, researchers will contact service users directly once their eligibility and any risk-related safety requirements have been established). The researchers will keep a record of potential participants to be contacted and the date and the name of the clinician with whom this was agreed. Researchers will ask the clinician who spoke to each service user to note the patient's agreement to be contacted by a researcher in their patient records. Those who agree will be contacted by a researcher with an information sheet and offer to answer any questions. Potential participants will be given at least 24 hours to consider whether they would like to take part, and then if still interested they will be consented by a researcher, who will also collect the baseline data. Participants will be offered £20 in cash as a thank you for taking part (£10 for the baseline interview, and £10 for the follow up interview at 8-12 weeks after baseline). If participants decline this money it will be returned to the study. Participants will be contacted by phone by a researcher 8-12 weeks after baseline in order to collect follow up data. At 6 months after baseline, participant data will be collected from patient records and clinical notes.

While many people find talking about their experiences to be helpful, some people may find that completing the questionnaire brings up issues that cause emotional distress. In this case the researcher will provide immediate emotional support to the participant, offer to pause or postpone the interview, and, if the participant asks, will contact a person of the participant's choice (e.g. current care coordinator, carer, friend, family member, colleague) for them.

If service users or carers report any untoward feedback, the researcher conducting the interview will confirm with the participant whether or not they would like the researcher to pass this on to the service or other relevant person. If the untoward feedback is of a nature that leads the researcher to be concerned for the safety of others, the participant will be informed that the feedback will be passed on to the relevant service or person to be addressed, but that if desired and possible they will remain anonymous.

STATISTICAL METHODS

We will provide descriptive statistics comparing the baseline characteristics of the CRT cohorts with and without ADU care within each of the five case studies and also for the

sample as a whole. We will explore baseline differences in demographics, diagnoses and symptom severity, severity of past mental health history and pathways into the crisis service using parametric and non-parametric tests as appropriate.

For the primary outcome we will compare the risk of readmission in the groups who do and do not receive ADU care using logistic regression adjusting for age, gender, main diagnostic group and a measure of severity.

We will compare satisfaction/ experience mean CSQ-8 scores in the two cohorts and use linear regression to adjust for important covariates. We will adjust for cluster (sampling unit being the ADU), and also test for effect modification by individual ADU. We will not make head to head comparisons of outcomes between ADUs.

For the economic evaluation we will also extract health service usage from clinical notes and apply unit costs from the sources described above, to estimate the costs incurred by participants during the 6-month follow-up period, and compare mean costs per patient with or without ADU care, controlling for confounders using baseline data.

We have calculated sample size to detect a 12-13% absolute reduction in the main outcome of re-admissions to the acute pathway at 6 months after baseline (using admission figures from our previous CRT research). Our CORE programme grant1 in crisis teams is powered at 80% to detect a 15% difference between trial arms (50% versus 35%). Recent data from London crisis services suggest baseline re-admission rates could be lower, at 40%. We have explored various sample size calculations, including different assumptions regarding this baseline readmission rate. These show that 310 people in each arm would afford 90% power to detect differences such as 50% versus 36.8%, 45% versus 32.0% or 40% versus 27.4%. Inflating for a design effect by 30% to accommodate the clustered study design requires 400 per arm. These numbers also afford greater than 90% power to detect an effect size or difference of 0.3 standard deviations in the client experience measure CSQ-8 (crisis team mean CSQ = 25, sd 6).

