Acute Day Units as Crisis Alternatives to Residential Care AD-CARE

Chief Investigator:

[name], UCL

Supported by:

NIHR HS&DR 15/24/17

Sponsored by:

[figure not shown]
University College London (UCL)

Protocol version number and date:

2 20/12/16

R&D / Sponsor Reference Number(s): 16/0576

Study Registration Number:

PROTOCOL VERSIONS

Version Stage	Versions No	Version Date	Protocol updated & finalised by;	Appendix No detail the reason(s) for the protocol update
Previous	1	25/10/16	[name]	N/A
Current	2	20/12/16	[name]	1

DECLARATIONS

The undersigned confirm that the following protocol has been agreed and accepted and that the investigator agrees to conduct the study in compliance with the approved protocol and will adhere to the Research Governance Framework 2005 (as amended thereafter), the Trust Data & Information policy, Sponsor and other relevant SOPs and applicable Trust policies and legal frameworks.

I (investigator) agree to ensure that the confidential information contained in this document will not be used for any other purposes other than the evaluation or conduct of the clinical investigation without the prior written consent of the Sponsor.

I (investigator) also confirm that an honest accurate and transparent account of the study will be given; and that any deviations from the study as planned in this protocol will be explained and reported accordingly.

Chief Investigator:		
Signature:		Date/
Print Name(in full):		
Position:		
On behalf of the Study Sponsor:		
Gaislans.		
Signature:		Date 15/11/2016
Print Name(in full): [name]		
Position: Research Portfolio Coordin	nator	

STUDY SUMMARY

Identifiers	
IRAS Number	201627
REC Reference No	
Sponsor Reference No	16/0576
Other research reference	
number(s) (if applicable)	
Full (Scientific) title	Acute Day Units as Crisis Alternatives to Residential Care
Health condition(s) or	
problem(s) studied	
Study Type i.e. Cohort etc	Observational cohort study, and qualitative study
Target sample size	Cohort study: n=800, qualitative study: n=55
STUDY TIMELINES	
Study Duration/length	Three years
Expected Start Date	01/07/16
End of Study definition	30/06/19
and anticipated date	
Key Study milestones	IRAS form submitted, REC attended, first participant recruited, final
	participant recruited
FUNDING & Other	
Funding	NIHR HS&DR
Other support	
STORAGE of SAMPLES	
(if applicable)	
Human tissue samples	N/A
Data collected / Storage	N/A

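### The primary readmission model in this non-randomised cohort omits pathway into crisis care, does not clearly include past mental health history, and leaves its severity measure undefined

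*Protocol*

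**What the plan says.** The study summary describes the cohort work as an "Observational cohort study, and qualitative study", so nobody is allocated to ADU care at random.

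Section 9 (Statistical Methods) first sets out the baseline comparison. It covers demographics, diagnoses, symptom severity, and then "severity of past mental health history and pathways into the crisis service using parametric and non-parametric tests as appropriate". The next paragraph gives the primary analysis of readmission, "using logistic regression adjusting for age, gender, main diagnostic group and a measure of severity". The severity measure is not named.

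The other two comparisons in section 9 are worded openly. The satisfaction score (CSQ-8) is adjusted for important covariates and costs for baseline confounders, and neither set is listed. Adjustment for cluster, the ADU being the sampling unit, is stated after the CSQ-8 sentence, so it is unclear whether it also covers the readmission model.

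The cohorts have different entry rules. For the ADU cohort, section 7.1 requires: "Have used the ADU for at least one week". For the comparators, section 4 says: "They must be receiving CRT home treatment when recruited, but could previously have been admitted to an inpatient ward during this episode". Section 4 also draws the comparators from "the same crisis pathway to participate in the parallel non-ADU cohort".

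**The concern.** In a cohort where clinical choice decides who attends the ADU, the adjusted odds ratio is only as good as its adjustment set. Previous admissions, and whether the person is stepping down from a ward, plausibly influence both referral to an ADU and later readmission. The protocol treats both areas as worth comparing between cohorts. It then fixes a shorter list for the analysis that answers the main question.

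This is more than detail left for a statistical analysis plan. The protocol names the primary covariates, and the list it names is narrow. An analysis that follows it to the letter would leave out a factor the study has singled out for comparison. A difference in readmission could then partly reflect who was sent where.

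**Working it through.** **1. The two lists side by side (section 9)**

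| Baseline area to be compared | In the primary model? |
|---|---|
| Demographics | Age and gender |
| Diagnoses | Main diagnostic group |
| Symptom severity | Possibly, as the one undefined severity measure |
| Severity of past mental health history | Possibly, as the same undefined measure |
| Pathways into the crisis service | No |

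The text uses the word severity for both symptoms and past history. The single measure could therefore be either, or a composite. Pathway has no such route into the model.

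**2. The protocol's own sample size**

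Inputs from section 9: 90% power; 50% v 36.8%, 45% v 32.0%, 40% v 27.4%; 310 per arm; 30% inflation. A two-sided 5% level is assumed, because none is stated. With d the difference and p̄ the mean of the two rates:

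n = [1.96·√(2p̄(1−p̄)) + 1.2816·√(p₁(1−p₁) + p₂(1−p₂))]² / d²

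With the continuity correction: n_c = (n/4)·[1 + √(1 + 4/(n·d))]²

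Without the correction this gives 295, 293 and 294. With it, 310, 308 and 310, so the stated 310 is reproduced. Then 310 × 1.30 = 403, close to the stated 400. The sample size is not in dispute. It supplies the yardstick of 12 to 13 points.

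**3. Gross effect of one omitted binary factor**

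Assumptions, none from the protocol: no true ADU effect; 35% readmission without the factor; odds ratio (OR) 2 to 3 for the factor; prevalence differing by 10 to 25 points between cohorts. The 35% is compatible with the protocol's rates: at a prevalence of one half, overall risk would be (35 + 51.9)/2 = 43% or (35 + 61.8)/2 = 48%, inside its 40% to 50% range.

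Risk with the factor = OR·o/(1 + OR·o), where o = 0.35/0.65 = 0.538.

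- OR 2: 1.077/2.077 = 51.9%, a risk difference of 16.9 points.
- OR 3: 1.615/2.615 = 61.8%, a risk difference of 26.8 points.

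Spurious difference = prevalence gap × risk difference:

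- smallest: 0.10 × 16.9 = 1.7 points, 13% of a 13-point target
- largest: 0.25 × 26.8 = 6.7 points, 51% of a 13-point target

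**4. A second set of assumptions**

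Here the non-ADU readmission rate is fixed at 40% or 50%, the OR runs from 1.5 to 3, and the effective size is 400/1.3 = 308 per arm. The false rejection rate is that of a two-sided 5% test with no true effect.

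| Prevalence, non-ADU v ADU | Spurious difference (points) | False rejection rate |
|---|---|---|
| 50% v 40% | 1.0 to 2.7 | 6% to 10% |
| 50% v 30% | 1.9 to 5.4 | 8% to 27% |
| 60% v 30% | 2.9 to 8.0 | 11% to 52% |

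The sign reverses if the factor is commoner in the ADU cohort. Both sets are gross figures. Age, gender, diagnosis and severity would remove part of the bias to the extent that they track the omitted factor.

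**5. Room in the model**

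Expected readmissions on the protocol's rates: 400 × (0.50 + 0.368) = 347; 400 × (0.45 + 0.32) = 308; 400 × (0.40 + 0.274) = 270. That is ample for a few extra terms.

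**The case against.** Several stronger readings are tempting, and the protocol does not support them.

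- **The cohorts are known to differ by design.** The protocol says only that baseline differences will be explored. Nothing points to a built-in difference in past history. For pathway, the different entry rules make a difference possible. Against that, comparators come from the same crisis pathway, section 9 calls both groups cohorts of the crisis resolution team (CRT), and ADUs also serve people leaving wards early (section 1). Step-down patients can therefore be in both cohorts.
- **ADU participants may arrive by any route.** No route is specified, which is not the same as every route being open.
- **Past history is certainly left out.** The undefined severity measure could be a past-history measure or a composite. What can be shown is the ambiguity, and an analysis plan that was not available for this review may resolve it.
- **The cost analysis is better adjusted than the primary outcome.** Its wording is more open, but it names no covariate, so it is not shown to be stronger.

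It is also fair to say that some residual confounding remains in any observational cohort under any covariate list, and that the magnitudes above rest on assumed inputs.

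These points limit the strength of the claim. They do not put pathway into the primary model or say what the severity measure is.

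**Conclusion.** The point holds in a limited form. The stated list omits pathway into the crisis service and does not clearly include severity of past mental health history, although the protocol plans to compare the cohorts on both. The readmission comparison is therefore open to residual confounding that could be reduced with factors already due for comparison.

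A reader might infer that the result is confounded beyond use. The protocol does not support that: neither the direction nor the size of any bias can be derived from it. Under the assumptions of step 3, one omitted factor would give a gross spurious difference of about 1.7 to 6.7 points against a target of 12 to 13. The wider assumptions of step 4 give 1.0 to 8.0. The net figure would be smaller to the extent that the listed covariates stand in for the missing factor.

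This is worth correcting before outcomes are seen, because the correction is cheap and the contrast is the study's primary one. It is not a fatal flaw, and the sample size is unaffected.

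**What to change.** Prespecify the primary logistic model with:

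- age, gender and main diagnostic group, as now
- symptom severity, with the instrument named
- past mental health history, with the measure named, for example previous psychiatric admissions
- pathway into crisis care, including whether there was an inpatient stay earlier in the current episode

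State that the cluster adjustment applies to the readmission model as well as to CSQ-8.

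Add a sensitivity analysis that restricts the ADU cohort to people who came through the CRT. If some ADU routes have no counterpart among the comparators, a regression term for route only extrapolates; the restriction shows whether the result depends on that.

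The cost is a few more terms, slightly wider intervals and a change of wording. With about 270 to 347 expected readmissions the model can carry them. One practical check is needed: the protocol gives no itemised list of baseline data, so confirm that an earlier inpatient stay in the episode is recorded or can be taken from the clinical notes already to be searched at 6 months.
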